17.1. Description of Statistical Methods

Nominal and ordinal scale data will be presented as counts (N) and percentages (%) in each of the categories analysed, with the denominator used to determine the percentages given.

The range of summaries for interval scale variables, in each of the categories analysed, will include: mean with standard deviation, median and lower and upper quartile, maximum and minimum value, as well as the number of people for whom estimates of basic statistics were made.

If graphical presentation of the data is necessary, box-plots (median, quartiles, range of outliers or minimum/maximum values) and/or graphs of averages with 95% confidence intervals will be used.

The distribution of the variables will be evaluated based on the quantile-quantile (Q-Q) plot and the results of the Shapiro-Wilk test. Homogeneity of variance will be assessed using Levene's test.

For the CRS-R and MOCA tests, and the C-Eye X MCSD and CFA tests, the results will be presented as:

- 1) the sum of scores for all subscales of the test,
- 2) the point value obtained in each subscale,
- 3) the percentage of the total score for all subscales of the test related to the maximum value possible for the test (23 points for the CRS- R test, 30 points for the MOCA test, 11 points for the MCSD test, 24 points for the CFA test),
- 4) the percentage value in each subscale related to the maximum value possible in the subscale.

In each subsequent visit following visit 1, the relative percentage increases in total and subscale scores will be shown for visit 1. In addition, from all consecutive visits, the sum total of the test and subscale scores for each test will be determined; the data will be presented as raw values (points) and percentages related to the sum total of the maximum possible value for the test/subscale.

Analysis of the results of each test over time (in 3 or 5 consecutive visits) will be carried out using analysis of variance with repeated measures and contrast analysis (for raw or transformed data) or Friedman analysis of variance – depending on the type of data distribution, for both raw data and transformed percentages.

For patients enrolled in Test 1, the percentages of total scores for all subscales of the test relative to the maximum value possible in the test will be used to compare the scores during the

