follow-up period (in 5 consecutive visits) obtained by the MCSD C-Eye X test with those of the CRS-R test. The analysis will be conducted using one-way analysis of variance (the type of test will be a factor) with repeated measures and contrast analysis. If the assumptions of normality of distribution are not met, an appropriate nonparametric method or logarithmic transformation or aligned rank transformation will be used. The relative percentage increases in total scores at the last visit relative to the Visit 1 and the summed (from all measurements over time) total scores relative to the summed maximum possible on a given test (%) will be compared using Student's t-test or Mann-Whitney U-test, depending on the type of data distribution.

For patients enrolled in Test 2, the percentages of total scores for all subscales of the test related to the maximum value possible in the test will be used to compare the results during the follow-up period (in 3 consecutive visits) obtained with the CFA C-Eye X test with the results of the CRS-R and MOCA tests. The analysis will be conducted using one-way analysis of variance (the type of test will be a factor) with repeated measures and contrast analysis. If the assumptions of normality of distribution are not met, an appropriate nonparametric method or logarithmic transformation or aligned rank transformation will be used. Relative percentage increases in total scores at the most recent visit relative to the Visit 1 and the summed (from all measurements over time) total scores relative to the summed maximum possible on a given test (%) will be compared using one-factor analysis of variance (the type of test will be a factor) with Tukey's post-hoc test or Kruskal-Wallis one-factor analysis of variance, with multiple comparisons tests of mean ranks for all samples, depending on the type of data distribution.

Passing-Bablok orthogonal regression will be used to evaluate the consistency of test scores (summed percentages of total scores for all subscales of the test related to the maximum possible value for the test) of the MCSD and CFA C-Eye X with the CRS-R and MOCA tests. In addition, Pearson's linear correlation coefficient or Spearman's rank coefficient will be determined depending on the distribution of the data. If the assumptions of normality of distribution are not met, an appropriate nonparametric method or logarithmic transformation will be used.

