The selection of appropriate methods will be discussed further in the Statistical Analysis Plan.

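### Two between-instrument summaries come from the same patients, but most of the tests named for them assume independent samples

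*Protocol*

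**What the plan says.** Protocol section 7 has each Test 1 patient take CRS-R and then MCSD on the same day, five times. Each Test 2 patient takes CRS-R, MOCA and CFA at three visits. Every comparison between instruments is therefore within patients.

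Section 17.1 defines two summaries per instrument. One is the change: "The relative percentage increases in total scores at the last visit relative to the Visit 1". The other is the score summed over visits, expressed as "percentages related to the sum total of the maximum possible value for the test/subscale". The tests named for comparing both summaries between instruments are:

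- Test 1: Student's "t-test or Mann-Whitney U-test, depending on the type of data distribution".
- Test 2: both "will be compared using one-factor analysis of variance (the type of test will be a factor"), with Tukey's post-hoc test, and as the alternative "Kruskal-Wallis one-factor analysis of variance, with multiple comparisons tests of mean ranks for all samples".

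Neither sentence mentions pairing or repeated measures. For the visit-by-visit percentages, the same paragraphs do: "The analysis will be conducted using one-way analysis of variance (the type of test will be a factor) with repeated measures and contrast analysis". If normality fails there, "an appropriate nonparametric method or logarithmic transformation or aligned rank transformation will be used". Section 17.1 also names Friedman's test for change over visits within one instrument. It ends: "The selection of appropriate methods will be discussed further in the Statistical Analysis Plan". Section 17.3 sets a two-sided 5% level.

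**The concern.** Mann-Whitney, one-factor ANOVA with Tukey, and Kruskal-Wallis with mean-rank comparisons all treat the instruments as if different patients had taken them. Only the t-test can be read as paired, and its form is not stated. These tests use the wrong variance for a within-patient difference. If the two scores correlate positively, they are conservative and lose power. If the correlation is negative, they reject too often.

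The secondary endpoint in section 4.1 is the difference between C-Eye X and behavioural results. A test of difference that is far too conservative could return a non-significant result that is then read as the instruments agreeing. Sample size was set by feasibility and budget (section 17.2), so the pairing is information that the study cannot easily replace.

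**Working it through.** **Inputs.** From the protocol: 45 observations per Test (17.2), two-sided 5% (17.3), two instruments at five visits in Test 1 and three instruments at three visits in Test 2 (section 7). The protocol gives no SD, effect size or between-instrument correlation ρ, and no power figure to reproduce. Assumed below: normal scores, equal SDs, a difference of 0.4 SD for power, and ρ from -0.2 to 0.7.

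**Step 1: standard error.** With s the ratio of the two SDs, the unpaired standard error divided by the correct one is √[(1+s²)/(1+s²-2ρs)]. At ρ = 0.5:
- s = 1: √(2/1) = 1.41
- s = 0.5: √(1.25/0.75) = 1.29
- s = 0.2: √(1.04/0.84) = 1.11

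At s = 1 the ratio is 1.20 for ρ = 0.3 and 1.83 for ρ = 0.7.

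**Step 2: true level.** For s = 1 the level of the unpaired test is about 2[1-Φ(1.96/√(1-ρ))]. At ρ = 0.5 this is 2[1-Φ(2.77)] = 0.6%. At ρ = -0.3, 0, 0.3 and 0.7 it is 8.6%, 5.0%, 1.9% and 0.04%.

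**Step 3: Test 1 by simulation** (20,000 replicates, all in %).

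| ρ | -0.2 | 0 | 0.1 | 0.3 | 0.5 | 0.7 |
|---|---|---|---|---|---|---|
| Mann-Whitney, level | 7.3 | 5.2 | 3.8 | 2.3 | 0.8 | 0.1 |
| Unpaired t, level | 7.4 | 5.2 | 3.8 | 2.1 | 0.7 | 0.05 |
| Mann-Whitney, power | 45 | 45 | 45 | 44 | 43 | 42 |
| Signed-rank, power | 38 | 44 | 48 | 58 | 73 | 91 |
| Unpaired t, power | 47 | 47 | 47 | 46 | 46 | 44 |
| Paired t, power | 39 | 46 | 50 | 60 | 75 | 92 |

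A noncentral-t calculation of paired t power gives 39.5, 45.9, 49.9, 60.2, 74.7 and 92.3%. Repeat simulations put the Mann-Whitney level at 4.3 to 5.2% for ρ = 0 and 1.9 to 2.3% for ρ = 0.3. With unequal SDs the gap narrows: at ρ = 0.5, Mann-Whitney against signed-rank is 66% against 84% for s = 0.5, and 71% against 80% for s = 0.2.

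**Step 4: Test 2 by simulation** (10,000 replicates, one instrument shifted, mean-rank comparisons in Bonferroni form, all in %). Power is for one pair.

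| ρ | -0.2 | 0 | 0.1 | 0.3 | 0.5 | 0.7 |
|---|---|---|---|---|---|---|
| Tukey, family-wise error | 8.2 | 5.1 | 3.7 | 1.4 | 0.3 | 0.0 |
| Tukey, power | 34 | 32 | 31 | 29 | 26 | 21 |
| Holm paired t, power | 26 | 30 | 35 | 45 | 61 | 86 |
| Mean-rank, power | 30 | 28 | 27 | 24 | 22 | 17 |
| Holm signed-rank, power | 24 | 28 | 32 | 41 | 58 | 84 |

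**Step 5: does another planned analysis cover this?** Each test has a fixed maximum M, so with complete data over k visits Σx/(kM) = (1/k)Σ(x/M). The summed percentage is therefore the mean of the visit percentages. If type of test is the within-patient factor, the planned repeated-measures ANOVA tests the same difference as a paired t-test on the summed score. A simulated set (45 patients, 2 instruments, 5 visits) confirms this: F = 9.5888 equals the paired t squared. With type of test as a between-patient factor, F = 2.3409 equals the unpaired t squared, and the cover is gone. No equivalent analysis is stated for the relative increase.

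**Step 6: the relative increase itself.** It was simulated as a ratio of log-normal scores. On the log scale: level SD 0.3, levels correlated 0.7 between instruments, growth mean 0.1 and SD 0.15, noise SD 0.1. When the increases correlate -0.15 / 0 / 0.15 / 0.27 / 0.36, the Mann-Whitney level is 6.8 / 5.5 / 3.6 / 2.4 / 1.7%. In a repeat with a 0.4 SD shift (4,000 runs; correlations -0.15 / 0 / 0.16 / 0.26 / 0.37), Mann-Whitney power is 47 / 48 / 48 / 47 / 47% against 39 / 45 / 51 / 57 / 64% for signed-rank. Strongly correlated levels do not imply strongly correlated increases.

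**The case against.** The other side does not dispute that the tests are misnamed. It disputes how much this matters.

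- **The largest gaps are not where the uncovered harm is.** Contrasts such as 42% against 91% come from plain scores at ρ = 0.7. For the simulated relative increase the gain is at most 64 - 47 = 17 points, and there is none at zero correlation or below. This stands.
- **Friedman can be weaker.** For plain scores with three instruments its overall power is 34% against 47% for Kruskal-Wallis at ρ = 0, and 38% against 45% at ρ = 0.1. For the simulated relative increase (3,000 runs) it is behind until the correlation reaches about 0.25. This stands for the overall test. For plain scores at ρ = 0 or above, Holm signed-rank pairs are no weaker than the mean-rank comparisons. At negative ρ the Kruskal-Wallis figure is flattered by its inflated level.
- **The relative increase is ancillary.** Section 4.1 describes comparing percentage scores, and the increase from Visit 1 appears only in section 17.1. The summary closest to section 4.1, the summed percentage, is the partly covered one. This stands and limits the consequence.
- **Aligned rank transformation can respect pairing.** It can, but it is one of several fallbacks, it belongs to the visit-level analysis, and it does not change the tests named for the two summaries.
- **A zero at Visit 1 makes the ratio undefined.** A paired method then drops the whole pair or triplet, and section 17.4 imputes nothing. This is a real cost of pairing, but it does not make an independent-samples test valid.
- **The SAP may put this right.** It was not available here. The protocol's closing reference to it promises further discussion but does not withdraw the tests named, and section 17.5 gives no procedure for reporting departures from the plan.

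**Conclusion.** The concern holds. For these two summaries section 17.1 names tests for independent samples although the data are matched, and it does so beside sentences that specify repeated measures. This is a wrong statement, not missing detail.

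The parametric analysis of the summed score is covered if data are complete and type of test is taken as the within-patient factor, which the protocol does not say outright. The relative increase has no cover, and the nonparametric route has only an unspecified one. There the true level may lie on either side of 5%: 6.8% down to 1.7% in the simulated relative increase, and further below 5% if the scores correlate strongly. These sizes depend on assumed correlations, SDs and distributions. Near zero correlation little is lost.

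With positive correlation the error is conservative, so it costs power and does not produce false positives. No power claim is affected, and agreement is assessed separately by Passing-Bablok regression and correlation. The point should be corrected, but it does not undermine the study as a whole.

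**What to change.** Change two sentences in section 17.1, for these two summaries only, and carry them into the SAP:

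- **Test 1:** name the paired t-test or the Wilcoxon signed-rank test.
- **Test 2:** name repeated-measures ANOVA or Friedman's test, with paired post-hoc comparisons adjusted for multiplicity, for example by Holm. The adjustment must stay: unadjusted paired contrasts gave a family-wise error of 12 to 13%, and Holm 4.1 to 5.0%.

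It would also help to state in the visit-level sentence that type of test is a within-patient factor, because the cover for the summed score depends on it.

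No new data or patients are needed. At zero correlation the paired t-test costs about 1 point of power (46% against 47%), and Friedman's overall test costs 47 - 34 = 13 points against Kruskal-Wallis. Patients whose ratio is undefined on one instrument drop out of that paired comparison, and their number should be reported.

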17.2. The Number of Participants

Due to the lack of rationale, it is not possible to statistically estimate the sample size. The number of participants (90 in 2 groups of 45) was chosen due to logistical feasibility and the Study's budget.

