17.3. The Level of Statistical Significance

A statistical significance level of $p < 0.05$ will be used. All tests will be two-sided.

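### Section 17.1 judges consistency by Passing-Bablok regression and a correlation, neither of which shows how far apart one patient's two percentage scores are

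*Protocol*

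**What the plan says.** Protocol section 17.1 gives consistency its own analysis, on the summed percentage scores: "Passing-Bablok orthogonal regression will be used to evaluate the consistency of test scores". It continues: "In addition, Pearson's linear correlation coefficient or Spearman's rank coefficient will be determined depending on the distribution of the data". It gives no acceptance limit for slope, intercept, correlation or individual difference, and no rule for calling two instruments consistent.

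The same section also compares the instruments' mean levels. Percentage scores over visits go into repeated-measures ANOVA with type of test as the factor. Summed percentages are compared by Student's t-test or Mann-Whitney (Test 1), or by ANOVA with Tukey's test or Kruskal-Wallis (Test 2). Further discussion of method selection is left to the SAP, which is not available here.

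Section 4.1 names the evaluation of differences between behavioural methods and C-Eye X as the secondary endpoint. It explains that percentage scores obtained by the patient are compared so that discrepancies become visible and can inform how patients are diagnosed.

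On size, section 17.2 states: "The number of participants (90 in 2 groups of 45) was chosen due to logistical feasibility and the Study's budget". Section 17.3 sets a two-sided 5% level.

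**The concern.** The aim in section 4.1 concerns two scores in one patient: does C-Eye X give a different picture from the behavioural scale, and by how much? The methods assigned to consistency answer other questions. Passing-Bablok regression estimates a constant offset (intercept) and a proportional one (slope). A correlation measures whether patients are ranked or spaced similarly, and it does not change if one instrument reads higher by a constant. Scatter of individual differences does not move the regression line away from identity. It only widens its confidence intervals, which makes it easier for them to cover 1 and 0.

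Nothing else listed in section 17.1 reports the spread of paired differences. Two instruments with equal means but large individual disagreement could therefore look satisfactory on every planned comparison of total scores. A reader could take that as support for interchangeable use in single patients.

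**Working it through.** **Inputs from the protocol.** 45 patients per test (section 17.2); two-sided 5% level (section 17.3); percentage scores on a 0–100 scale (section 17.1). There is no sample-size calculation to reproduce: "Due to the lack of rationale, it is not possible to statistically estimate the sample size".

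**Assumptions, because the protocol gives no values.** SD 15 percentage points for both instruments, equal means, bivariate normal scores, correlation r = 0.5 as the main case. The reading tested is also an assumption: consistent means that the 95% interval for the slope contains 1, the interval for the intercept contains 0, and the correlation is significant.

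**Step 1: when is the correlation significant?** At n = 45 the critical |r| is 0.294. With a true r of 0.5 it is exceeded in about 95% of studies.

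**Step 2: how often do both regression intervals cover identity?** In simulation with the standard rank-based intervals, r = 0.5 and no bias: 92%.

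**Step 3: both together.** 88% in simulation (0.875), so about nine studies in ten. With SD 18 and scores rounded to the actual summed scales (115/55, 69/72 and 90/72 points), the figures are 88%, 87% and 89%.

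**Step 4: how far apart are one patient's scores in that case?** With equal SDs, the SD of the paired difference is SD × √(2(1 − r)), and the limits of agreement are ±1.96 times that.

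| r | SD of difference (SD 15) | 95% limits, SD 15 | 95% limits, SD 18 |
|---|---|---|---|
| 0.5 | 15 × √1.0 = 15.0 | ±29.4 | ±35.3 |
| 0.7 | 15 × √0.6 = 11.6 | ±22.8 | ±27.3 |
| 0.9 | 15 × √0.2 = 6.7 | ±13.1 | ±15.8 |

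At r = 0.7 and r = 0.9 without bias, the regression intervals also cover identity in 93% of studies. The pass rate thus hardly changes while the limits of agreement more than halve from the first row to the last.

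**Step 5: would the mean comparisons show it?** No. The true mean difference is zero, so a paired test is significant in about 5% of studies and an unpaired one less often.

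**Step 6: what would the proposed figures show?** At SD 15 and r = 0.5 the standard error of each limit is about 15 × √(1/45 + 1.96²/(2 × 44)) = 15 × 0.257 = 3.85. With t = 2.015 on 44 degrees of freedom, the 95% interval is ±7.8 points around a limit near ±29. With equal means and SDs, Lin's coefficient equals r, so 0.5. Both would make the poor individual agreement plain with 45 patients.

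**The case against.** The strongest reply is that the protocol nowhere says that intervals covering 1 and 0 amount to agreement. It says the regression will be used to evaluate consistency and that a coefficient will be determined. Acceptance limits are commonly left to a SAP, and the secondary endpoint is the evaluation of differences, so consistency is not a success criterion. This stands. The 90% figure is conditional on an inferred reading, and the absence of a margin in the protocol is not a fault in itself. What remains is the choice of method: limits on slope, intercept or correlation added in the SAP would still not measure individual differences.

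Passing-Bablok regression is also an established method-comparison technique for constant and proportional bias. That stands too, and is why it should be kept as a description.

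Two stronger readings are tempting, and neither is supported.

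- A reader might infer that unrelated instruments would usually look consistent. Regression alone does cover identity in about 93% of studies at zero correlation, but only with equal means and equal spread. At SD ratios of 0.8 and 1.25 this falls to about 65%, and at 0.7 and 1.5 to 38% and 26%. Once the planned correlation must also be significant and positive, about 2% pass even with equal spread.
- A reader might infer that a systematic bias would go unseen. The regression does miss a shift of 0.5 SD (7.5 points at SD 15) in 86%, 81% and 54% of studies at r = 0.5, 0.7 and 0.9. But the mean comparisons in the same section would usually find it: 71–87% if unpaired and 91–100% if paired, over that range of r.

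**Conclusion.** The point holds in a limited form. The methods that section 17.1 assigns to consistency describe offset, scaling and association, and no planned analysis in that section quantifies the within-patient difference that section 4.1 sets out to capture. Under the usual reading of these methods, about 90% of studies with 45 patients would look consistent while individual scores differ by up to about 29 points either way in 95% of patients (SD 15, r = 0.5, no bias). SD, correlation, normality and the reading itself are assumptions. With r = 0.9 the limits shrink to about ±13 points, so the size of the problem depends on a correlation the protocol does not give. This is worth correcting, but it does not threaten a stated success criterion, and the documents do not show that the sponsor will claim agreement from a non-significant result.

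**What to change.** In section 17.1, and correspondingly in the SAP, add for each instrument pair (MCSD with CRS-R; CFA with CRS-R; CFA with MOCA):

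- the patient-level paired difference in summed percentage score, with its mean and 95% confidence interval;
- Bland-Altman 95% limits of agreement with their confidence intervals;
- one absolute-agreement coefficient, either Lin's concordance coefficient or an absolute-agreement ICC.

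Base any statement on consistency on these figures. Keep Passing-Bablok regression and the correlation as descriptions of scaling and association. Drop the word orthogonal, since Passing-Bablok is a rank-based method and not orthogonal regression. Add one sentence saying that an interval including 1 or 0, or a significant correlation, is not evidence of agreement.

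The cost is a change of wording and slightly more analysis on data already collected, with no extra visits or patients. The downside for the sponsor is that reported agreement may look less favourable.

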17.2. The Number of Participants

Due to the lack of rationale, it is not possible to statistically estimate the sample size. The number of participants (90 in 2 groups of 45) was chosen due to logistical feasibility and the Study's budget.

17.3. The Level of Statistical Significance

A statistical significance level of $p < 0.05$ will be used. All tests will be two-sided.

